### **3.3. The baseline and follow-up examinations**

The baseline and follow-up examinations after 12 and 24 months will be carried out in the residential home by a single trained examiner. A portable dental chair, an intra-oral LED light, disposable dental mirrors and CPI probes will be used in the examination.

For each tooth that is not indicated for extraction, status of its crown and its root will be assessed and recorded separately. Caries diagnosis is based on visual and tactile inspection. No radiograph will be taken. Plaque and food debris that obscures visual inspection of the tooth surfaces will be removed. Four surfaces (mesial distal, buccal and lingual) per tooth will be examined and the status will be recorded using the following codes which basically follow the criteria recommended by the International Caries Detection and Assessment System (ICDAS II) Coordinating Committee (2009).

The oral hygiene status of the subject will be assessed and recorded by using the Visible Plaque Index (Ainamo & Bay, 1975). The presence or absence of visible plaque will be recorded on four surfaces (mesial, distal, buccal and lingual) per tooth.

The gingival status of the subject will be assessed and recorded using by the Gingival Bleeding Index (Ainamo & Bay, 1975). The presence or absence of bleeding within 10 seconds after running a probe across the gingival margin will be recorded on four surfaces (mesial, distal, buccal and lingual) per tooth.

Other information that will be recorded included whether the subject normally wears a removable partial denture or not, and the subject's general health status and medications that affect saliva flow rate.

The same examiner will carry out all the baseline and follow-up examinations without knowing the study group assignment of the subjects. It has been shown that good intra-examiner reproducibility can be achieved after training (Tan et al., 2010) and a random sample of 10% of the subjects will be re-examined during each examination to monitor intra-examiner reproducibility.

At the examinations, the subjects will be asked to report on their oral hygiene practices, use of fluoridated toothpaste and other topical fluoride agents, and use of dental services during the study period.

### **3.4. Interventions**

Oral health education talk and instructions on how to keep good oral hygiene will be provided at baseline and every year to all the elders in the selected residential homes. Standard fluoride toothpaste with 1000-1500 ppm fluoride will be provided free to all the elders in the selected residential homes over the 24-month study period.

After the baseline examination, subjects satisfying the inclusion criteria of the study will be stratified into two groups according to the number of natural teeth in their mouth, those with 12 or fewer teeth and those with 13 or more teeth. The subjects will then be assigned to one of the two study groups by a research assistant using a block randomization method with a block size of 6. The stratified randomization procedure will help to ensure that

the numbers of teeth involved in the two study groups are balanced. The group assignment of the study subjects will be concealed and placed in a sealed envelope, and will not be made known to the examiner who evaluate the study outcomes.

The interventions for the two study groups will be provided by other dentists and are described below:

Group 1 – plaque on the root surfaces of all teeth in the subject’s mouth will be removed by a small brush and a 38% SDF solution (Saforide, Toyo Chemical, Japan ) will be applied onto the root surfaces using a microbrush/applicator. This will be repeated every year.

Group 2 – plaque on the root surfaces of all teeth in the subject’s mouth will be removed by a small brush and a 10% povidone iodine solution (Betadine, Mundipharma, Switzerland) will be applied, then followed by application of a 5% sodium fluoride varnish (Duraflor, Medicom, Canada) using a microbrush/applicator. This will be repeated every 4 months.

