### **3. Methods and Materials**

#### **3.1. Study population**

The study population of this proposed clinical trial is adults aged 60 years and above living in residential care homes or attending long-term care facilities in Hong Kong. The subject inclusion criteria are:

1. have at least 6 teeth which are not indicated for extraction, and
2. have basic self-care ability.

Adults with one or more of the following conditions will be excluded:

1. have serious debilitating health/medical conditions, and
2. have cognitive problems or major problems in communication.

About 10 residential care homes or long-term care institutions served by NGO dental outreach teams in various districts with different background, such as private or publicly funded homes, will be selected by the PI in consultation with the NGOs. All elders living in the selected residential homes will be invited to attend a free dental examination. Elders fulfilling the inclusion criteria will be invited to participate in this study and informed written consent will be obtained before commencement of the study. Dental treatments other than the study interventions will be provided by dentists from the NGOs which serve the residential homes.

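### Section 3.4 fixes one block size of 6 and does not state that the next assignment is hidden from the person who assigns; a cheap change would close the gap

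*Protocol*

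**What the plan says.** Protocol section 3.4 sets out allocation in four steps.

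- **Timing.** "After the baseline examination, subjects satisfying the inclusion criteria of the study will be stratified into two groups". Assignment therefore comes after the baseline examination and the eligibility check. Section 3.1 adds that written consent is obtained before the study begins.
- **Strata.** There are two, "those with 12 or fewer teeth and those with 13 or more teeth". Residential home is not a stratum.
- **Method.** Subjects are "assigned to one of the two study groups by a research assistant using a block randomization method with a block size of 6". With 166 per group planned in section 3.2, allocation is 1:1, so each block holds three elders per group.
- **Concealment.** "The group assignment of the study subjects will be concealed and placed in a sealed envelope, and will not be made known to the examiner". The examiner meant here is the one responsible for outcome assessment.

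On treatment, "The interventions for the two study groups will be provided by other dentists". One group receives a single agent yearly and the other receives two agents every 4 months, so those who treat can tell the groups apart.

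Section 3.4 does not say who generates or holds the list, whether envelopes are prepared and numbered in advance, when they are opened, or in what order examined elders are entered.

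**The concern.** Two safeguards need to be kept apart. Keeping the examiner unaware protects outcome assessment, and the protocol provides for that. Allocation concealment protects the make-up of the groups: whoever enters the next elder must not be able to foresee the group. On this the protocol is unclear. The assigner works with one constant block size that is written in the protocol, may have made every earlier assignment in the stratum, and is not named as unaware of the next one.

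Several eligible elders in one home may be awaiting assignment with lesions, plaque and health already recorded. If the next slot can be deduced, the choice of who takes it could depend on caries risk. Stratifying on number of teeth does not balance those other factors, and the two-sample t-test in section 3.5 has no stated adjustment for them. In a non-inferiority comparison, sending lower-risk elders to the test group makes a false claim easier.

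**Working it through.** **Inputs.** Section 3.4: block size 6, two strata. Section 3.2: 1:1 allocation, 332 subjects, margin 0.8 surface, SD 2.0, two-sided 95% interval (one-sided 0.025), power 90%, 133 evaluable per group, 20% dropout.

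**The plan's own figure.** The normal approximation gives 2 × (1.960 + 1.282)² × 2.0² / 0.8² = 131.4, so 132 per group. The noncentral t calculation gives 133, as stated. 133 / 0.80 = 166.25, stated as 166. The sample size is not affected by this point.

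**Deducible assignments.** A 3:3 block has 20 equally likely orderings. An assignment is certain once one group has used its three places.

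| Position in block | Probability certain | Probability that the best guess is right |
|---|---|---|
| 1 | 0 | 0.5 |
| 2 | 0 | 0.6 |
| 3 | 0 | 0.6 |
| 4 | 0.1 | 0.7 |
| 5 | 0.4 | 0.7 |
| 6 | 1.0 | 1.0 |
| Sum | 1.5 | 4.1 |

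The best guess is always the group that is behind. Certain: 1.5 / 6 = 25.0%, which agrees with the closed form 2m/(m + 1) = 6/4 = 1.5 for m = 3. Best guess right: 4.1 / 6 = 68.3%. Over 332 subjects, 0.25 × 332 = 83 assignments are certain; a simulation allowing for unfinished last blocks gives about 81.

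**Illustrative effect.** Assume every certain slot is steered in favour of the test group: an elder with an expected count d below average goes into each certain test slot, and one d above average into each certain control slot. A quarter of each group is affected, so the difference shifts by 2 × 0.25 × d = 0.5d. The standard error is 2.0 × √(2/133) = 0.245. At a true difference of 0.8, the false-claim rate is P(Z > 1.96 − shift/0.245).

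| d (assumed), surfaces | Shift, surfaces | Shift / margin | False non-inferiority rate |
|---|---|---|---|
| 0 | 0 | 0% | 2.5% |
| 0.1 | 0.05 | 6% | 4.0% |
| 0.25 | 0.125 | 16% | 7.3% |
| 0.5 | 0.25 | 31% | 17% |

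**Effect of varying the blocks.** In a simulation of 166 subjects in a stratum, block sizes were drawn at random from 4, 6 and 8, and the guesser knew the possible sizes but not the size of each block. About 2% of assignments were certain, against 25%. Best guessing still succeeded about 68% of the time, because backing the group that is behind works whatever the block size.

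**The case against.** The strongest reply is that the protocol does describe concealment. Placing the assignment in a sealed envelope and withholding it from the examiner are two statements joined together. A reader might infer that the envelope hides the group only from the examiner; the text does not say that. What stands is narrower: the examiner is the only party named, and concealment from the assigner is not stated.

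A reader might also infer that a quarter of assignments are known in advance. That figure is conditional. It applies to someone who knows the block size and has followed every earlier assignment in that stratum. If past assignments are hidden from that person, none is certain. If the assigner holds the list, all are knowable and block size hardly matters. The protocol does not say which case applies, nor does the text show that the block size was public during recruitment.

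Two further routes are weakly supported. The treating dentists learn past assignments, but the protocol gives them no part in eligibility, enrolment or entry order. The exclusion "have serious debilitating health/medical conditions" calls for judgement, but nothing says that eligibility may be reopened after the examination.

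The false-claim rates assume steering of every certain slot, always in one direction. Steering on best guesses as well would give larger rates, but on still stronger assumptions about conduct, and nothing in the protocol points to such conduct. Section 3.5 also compares active lesions, oral hygiene and gingival status between groups at baseline, so large steering would probably be visible, although no adjustment is stated.

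These replies remove any claim of demonstrated bias. They leave the gap in the stated allocation procedure.

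**Conclusion.** The point holds as a low-cost improvement to a stated procedure. A fixed block size of 6, applied by a research assistant not named as unaware of the next assignment, lets an informed observer deduce on average 25% of assignments and guess 68% correctly. Both figures are exact for complete 3:3 blocks and depend on the observer tracking each stratum.

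Because the baseline examination and eligibility come first, what remains open is mainly the order of entry, which the protocol neither fixes nor leaves explicitly open. The rates of 4.0%, 7.3% and 17% are upper bounds for steering confined to deducible slots. They rest on assumed risk differences and should be read as an illustration of why the gap is worth closing.

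**What to change.** Amend section 3.4 in three parts. The first two are essential; the third supplements them.

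1. **Independent list.** Existing staff who do not recruit, examine, assign or treat generate and hold the list. They prepare sequentially numbered, sealed, opaque envelopes for each tooth-number stratum in advance.
2. **Fixed order of entry.** The research assistant opens the next envelope only after consent, eligibility and stratum are recorded, taking elders in the order of their baseline examination.
3. **Varying blocks.** Replace the fixed size of 6 with randomly varying sizes, for example 4, 6 and 8, not disclosed to those who recruit, examine, assign or treat. This removes most certain assignments but not the advantage of guessing, so it cannot stand in for the first two parts.

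The cost is minor preparation work and a protocol wording change, with no added subjects, visits or staff. The largest possible imbalance at the end of a stratum rises from 3 to 4 subjects, which is negligible with 166 per group.

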### **3.5. Statistical analysis**

The collected data will be entered into a computer and analyzed using the software SPSS for Windows version 20. T-test and Chi-square test will be used, as appropriate, to assess the differences in the distribution of age, gender, denture wearing, number of remaining teeth, number of active caries lesions, oral hygiene practice and status, and gingival status at baseline between the two study groups.

The number of root surfaces with new caries found at each follow-up examination will be calculated. Two-sample t-test test will be used to find out if there are statistically significant differences between the two study groups in the number of tooth surfaces that have developed new dental caries. Both intention-to-treat and per protocol analysis will be performed to compare the effectiveness and efficacy of the two study preventive methods.

Two-level, tooth surface and subject, survival analysis will be used to assess the rates of arrest of active root surface caries in the two study groups (Wong et al. 2005). The statistical significance level for all tests will be set at 5%.

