### **Null hypotheses to be tested:**

1. In this non-inferiority randomised controlled trial, the primary hypothesis to be tested is that 4-monthly application of 10% povidone iodine solution and 5% sodium fluoride varnish is at least not appreciably worse than a 38% SDF solution in preventing new dental root caries development over a 24-month period. The primary outcome measure is the development of new root surface caries lesions in the teeth of the elders.
2. The secondary hypothesis to be tested is that 4-monthly application of 10% povidone iodine solution and 5% sodium fluoride varnish is at least not appreciably worse than a 38% SDF solution in arresting active root caries over a 24-month period. The secondary outcome measure is the conversion of active (soft/demineralized) root surface caries lesions to inactive (hard/remineralized) lesions.

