#### **3.2. Sample size**

This non-inferiority trial aims to compare the caries preventive effect of applications of 38% SDF solution and that of combined 10% povidone iodine solution and 5% NaF varnish. A non-inferiority margin of 0.8 surface for the difference in the mean number of new caries surfaces over the 24-month study period is considered not clinically significant. The estimated sample size is based on the lower limit of the 2-sided 95% confidence interval for the difference set above the non-inferiority margin and the statistical power of the study being set at 90% ( $\beta=0.10$ ). The estimated standard deviation is 2.0, based on the results of a previous clinical trial conducted in Hong Kong (Tan et al., 2010). Using the statistical power analyses software, G\*Power (version 3.1.7; Franz Faul, Universität Kiel, Kiel, Germany), the total required number of elders in each group is calculated to be 133. Allowing for a drop-out rate of 20% in this 24-month study, an initial sample size of 166 subjects in each group or a total of 332 subjects is needed.

With a total sample size of 332 subjects and an estimated mean number of one untreated early/shallow root caries lesions per subject (Department of Health, 2013), there will be 332 root caries lesions in total or 166 lesions in each study group for caries arrest treatment. With this sample size, there is approximately 85% power that an absolute 15% difference in dental caries arrest rates between two groups can be shown to be statistically significant at the 5% level using Chi-square test when the overall success rate of the caries arrest treatment is around 80%.

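### As written, the 24-month t-test cannot use an elder who missed the 24-month examination, nor lesions already recorded at 12 months, so the promised intention-to-treat analysis may amount to a completers' analysis

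*Protocol*

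**What the plan says.** Protocol section 3.5 (Statistical analysis) states that "The number of root surfaces with new caries found at each follow-up examination will be calculated". It then names the comparison: "Two-sample t-test test will be used to find out if there are statistically significant differences between the two study groups". On analysis populations it adds that "Both intention-to-treat and per protocol analysis will be performed", without defining either population.

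The timing comes from elsewhere. Section 3.3 places the follow-up examinations at 12 and 24 months. The primary hypothesis in section 2 concerns the effect "in preventing new dental root caries development over a 24-month period". Section 3.2 sets "A non-inferiority margin of 0.8 surface for the difference in the mean number of new caries surfaces over the 24-month study period".

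Section 3.2 then raises 133 elders per group to 166, with the words "Allowing for a drop-out rate of 20% in this 24-month study".

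No sentence says how an elder without a 24-month examination enters the intention-to-treat comparison.

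**The concern.** A two-sample t-test needs one value per person. At 24 months that value is the count of new carious root surfaces, and an elder not examined then has none. Someone who leaves after month 12 may already have several new lesions on record. Those lesions are part of the 24-month total, yet the named test has no place for them. The population promised (everyone randomised) and the method named (which can use only those with a final count) do not fit together unless a further step is added.

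The stake is the non-inferiority conclusion. If elders with more new caries are more likely to leave, high counts disappear from the comparison. If more of them disappear from the povidone iodine plus varnish group, the observed difference is too small, and a small difference is what supports the claim. The opposite pattern would make the claim harder to reach.

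**Working it through.** **1. The plan's own figures.** Inputs from section 3.2: margin 0.8, SD 2.0, two-sided 95% interval, power 90%. The normal approximation gives n = 2 × (1.96 + 1.2816)² × 2.0² / 0.8² = 131.3, so 132 per group. The exact t calculation gives 133 (power 0.9015; 132 gives 0.8993), which reproduces the stated figure. For drop-out, 133 / 0.8 = 166.25, against 166 stated. The power calculation therefore counts about 133 of 166 per group as analysed, and 332 × 0.20 = 66.4 elders are expected to have no final count.

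**2. Precision at 133 per group.** SE = 2.0 × √(2/133) = 0.245, and the interval half-width is 0.483. Non-inferiority needs an observed difference below about 0.80 − 0.48 = 0.32.

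**3. Leaving unrelated to caries.** There is no bias, and simulation gave a false-claim rate of 2.4%. The gain from using 12-month counts is roughly 166 × p × r² elders per group, where p is the proportion leaving after month 12 and r the correlation between the 12- and 24-month counts. With p = 0.05 and r = 0.6 this is 3.0; with p = 0.10 and r = 0.8 it is 10.6. Both p and r are assumed.

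**4. Arm-specific patterns** (assumed; normal counts, 166 per arm, true difference 0.8, completers only):
- Drop-out 20% in both arms, leavers 1 surface worse in both: 2.4%, no bias.
- Drop-out 20% in both arms, only test-arm leavers worse by 0.5, 1 or 2 surfaces: completers' difference 0.70, 0.60 or 0.40; false-claim rate 5.9%, 12.4% or 37.2%.
- Drop-out 20% in both arms, only control-arm leavers 1 surface worse: 0.3%, a bias against non-inferiority.
- Leavers 1 surface worse in both arms, drop-out 30% test and 10% control: 12.5%. With 10% test and 30% control: 0.3%.

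**5. The same leaving rule in both arms, skewed counts** (assumed). Counts are negative binomial with a common dispersion k, SDF-arm SD 2.0 and true difference 0.8. About 10% to 13% leave after month 12, with log-odds rising by 0.15 or 0.30 per surface recorded at 12 months. The protocol gives no SDF-arm mean, so it is varied. The test-arm variance is μ + μ²/k, with k = m²/(4 − m), SDF mean m and μ = m + 0.8. The SE is √[(4 + test variance)/133], and the false-claim rate is Φ((0.8 − d)/SE − 1.96), where d is the completers' difference.

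| SDF mean | d (slope 0.15 / 0.30) | Rate at SE 0.245 | SE with larger test-arm SD | Rate at that SE |
|---|---|---|---|---|
| 0.7 | 0.63 / 0.45 | 10% / 30% | 0.394 | 6% / 14% |
| 1.0 | 0.71 / 0.59 | 6% / 14% | 0.342 | 4% / 9% |
| 1.5 | 0.76 / 0.68 | 4% / 7% | 0.303 | 3% / 6% |

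A further run, with baseline loss of 5% to 10%, gave d from 0.37 to 0.76. At d = 0.37 and SE 0.394 the rate is Φ(0.43/0.394 − 1.96) = Φ(−0.87), or 19%. The overall range with the appropriate SE is thus about 3% to 19%.

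Estimating the 24-month means with the help of the 12-month counts returned about 0.80. Carrying the 12-month count forward as the final value gave 0.61 to 0.74, which still leans towards non-inferiority. With normal counts and equal SD, the same leaving rule left the completers' difference at 0.80, so the shrinkage depends on skewness.

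**The case against.** The strongest reply is that the protocol never says these elders are dropped. It promises intention-to-treat, and imputing or carrying forward a value before the t-test would fit its wording. Population definitions and missing-data rules are commonly left to a statistical analysis plan, which may exist. A reader might infer that section 3.5 orders separate tests by visit and discards 12-month lesions. The text does not support that: the sentence on each follow-up examination concerns only the calculation of counts, and the 20% allowance is ordinary planning. This part of the reply stands, so the point has to be conditional.

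A reader might also infer that the result will lean towards non-inferiority. The documents do not support this either. They say nothing about why elders leave, loss in this population may be largely unrelated to caries, and step 4 shows patterns with no bias and with the opposite bias.

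The sizes are assumption-driven. Holding the SE at 0.245 overstates them, because skewed counts with a higher mean also have a larger SD. The recovery of 0.80 is by construction, since simulated leaving depended only on the 12-month count, which is what the proposed model assumes.

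What does not fall away is that the one method named cannot, by itself, use these elders, and that an obvious repair such as carrying forward is not neutral.

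**Conclusion.** The point holds as a conditional one. The t-test is the only method named for the primary count, and the hypothesis and margin are set at 24 months. Unless another rule is applied, about one fifth of those randomised would have no weight in the 24-month comparison, and their 12-month lesions would go unused. The cost is small if leaving is unrelated to caries. If leaving depends on caries, the bias can take either direction. With a common leaving rule and skewed counts it favours non-inferiority, with illustrative false-claim rates of about 3% to 19% against 2.5%. That range depends on the SDF-arm mean, the skewness and the drop-out pattern, none of which the protocol gives. It shows that the choice can matter and is not an estimate for this trial. The change is worth making because it is cheap and assumes less about the missing data, not because an error has been shown.

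**What to change.** For the intention-to-treat analysis, replace the t-test with one longitudinal model of the cumulative count of new root caries surfaces at 12 and 24 months. Include group, visit, group-by-visit interaction and the tooth-number stratum used in randomisation. Because the counts are skewed, use an unstructured covariance estimated separately by group, or robust standard errors. Include every randomised elder with at least one follow-up examination. Read the 24-month mean difference and its 95% confidence interval against the 0.8 margin. Keep the 24-month completers' t-test as a sensitivity analysis. If a statistical analysis plan already holds a rule for elders without a final examination, section 3.5 should refer to it.

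The cost is a change of wording and slightly more analysis work; no additional data are needed. The model relies on data being missing at random given the 12-month count, which is weaker than what a completers' comparison requires but cannot be verified. Elders lost before month 12 are still not represented, so the numbers lost before and after that visit should be reported by group.

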## **Summary**

Dental caries (tooth decay) is common among elders in Hong Kong and worldwide, placing heavy burden on the dental care services. There is an urgent need to develop effective and practical management approaches to improve the dental caries situation in the elders, especially among those living in residential care homes whose dental caries status is amongst the worst. The main objective of this study is to compare the effectiveness and cost-effectiveness of 4-monthly application of 10% povidone iodine solution followed by 5% sodium fluoride varnish with those of annual application of 38% silver diammine fluoride solution on the prevention of new dental root caries in elders. A secondary objective is to compare the effectiveness of the two interventions mentioned above on arresting (halting the progression) active root surface caries in the elders, thus avoiding the need for placing dental restorations.

This proposed study is a randomized double-blind controlled clinical trial with 24-month follow-up. A total of 332 elders aged 60 years or above living in residential homes or attending long-term care facilities in different districts in Hong Kong will be recruited. This sample size is sufficient for appropriate statistical analysis of non-inferiority with power set at 90% and allowing for a 20% dropout. Baseline clinical examination will be conducted by a single calibrated examiner in the homes using an intra-oral LED light, dental mirrors and probes. Subjects will be randomly allocated to one of the two study groups: 1) positive control - receive annual application of 38% silver diammine fluoride solution; and 2) test - receive application of 10% povidone iodine solution followed by application of 5% sodium fluoride varnish every 4 months. Follow-up examinations will be carried out after 12 and 24 months by the same blinded examiner to assess the clinical outcomes, i.e. whether new dental caries has developed and whether the active root surface caries lesions found at baseline have become arrested (hardened). Results of this study will provide the much needed evidence to guide the dental professionals in Hong Kong and worldwide in deciding on the most appropriate intervention for the prevention and management of dental caries in the older adults, especially those living in institutions.

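### The only analysis stated for the primary outcome is a t-test for a difference; the non-inferiority rule that sized the trial does not appear in section 3.5

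*Protocol*

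**What the plan says.** Section 2 of the protocol frames the trial as non-inferiority: "In this non-inferiority randomised controlled trial, the primary hypothesis to be tested is that 4-monthly application of 10% povidone iodine solution" with fluoride varnish "is at least not appreciably worse than a 38% SDF solution in preventing new dental root caries development over a 24-month period". This claim stands under a heading that calls it a null hypothesis.

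Section 3.2 gives the margin, "A non-inferiority margin of 0.8 surface for the difference in the mean number of new caries surfaces over the 24-month study period", and bases the sample size on "the lower limit of the 2-sided 95% confidence interval for the difference set above the non-inferiority margin", with 90% power and an SD of 2.0. The result is 133 per group, raised to 166 per group (332 in total) for 20% dropout. The Summary agrees: "This sample size is sufficient for appropriate statistical analysis of non-inferiority with power set at 90"%.

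Section 3.5 then states the analysis of new caries: "Two-sample t-test test will be used to find out if there are statistically significant differences between the two study groups". It adds "Both intention-to-treat and per protocol analysis will be performed to compare the effectiveness and efficacy of the two study preventive methods" and "The statistical significance level for all tests will be set at 5"%. It mentions neither the margin nor a confidence interval, and nothing elsewhere in the protocol ties the t-test to the margin.

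**The concern.** A test for a difference asks whether the data are incompatible with zero difference. A non-inferiority analysis asks whether they are incompatible with an excess as large as the margin. Failing to reject the first null is not evidence for the second claim. Section 3.5 is not silent on the primary outcome, which could have been left to an SAP; it names a procedure, and that procedure answers a different question from the one in section 2.

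The decision on the primary outcome is at stake. A trial could show no significant difference and still fail the criterion on which it was sized, and section 3.5 does not say which result governs. Reading non-significance as success would also reward noise, because the wider the interval, the easier it is to be non-significant.

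Two smaller wording gaps add to this:

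- Section 3.2 gives no order of subtraction and no sign for the margin. New caries is a harm, so a lower limit above the margin works only for SDF minus test with a margin of -0.8.
- Section 2 labels as a null hypothesis what is the alternative in a non-inferiority test.

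**Working it through.** **Inputs (protocol section 3.2):** margin 0.8 surface; SD 2.0; two-sided 95% CI (one-sided 0.025); power 90%; 133 evaluable and 166 randomised per group. The true difference is not stated. Zero is assumed, and it reproduces the stated number.

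**Reproducing the sample size.** By normal approximation, n = 2 × SD² × (1.960 + 1.282)² / 0.8² = 2 × 4 × 10.51 / 0.64 = 131.3, so 132 per group. With the exact noncentral t and standardised margin 0.8/2.0 = 0.4, power is 89.9% at 132 and 90.1% at 133, so 133 is reproduced. Dropout: 133/0.8 = 166.25, stated as 166. The trial is therefore sized for a CI against the margin.

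**The two rules at the planned size.** Let D be the observed difference in mean new caries surfaces, test minus SDF.

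- SE = SD × √(2/n); half-width h = t(0.975; 2n − 2) × SE.
- Section 3.5: not significant if −h < D < h.
- Section 3.2, in this direction: non-inferior if D + h < 0.8, that is D < 0.8 − h.

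| | 133 per group | 166 per group (no dropout) |
|---|---|---|
| SE | 2 × √(2/133) = 0.2453 | 2 × √(2/166) = 0.2195 |
| h | 1.969 × 0.2453 = 0.483 | 1.967 × 0.2195 = 0.432 |
| Non-inferiority cut-off, 0.8 − h | 0.317 | 0.368 |
| Non-significant but not non-inferior | D from 0.317 to 0.483 | D from 0.368 to 0.432 |
| Upper limit when D = h | 0.966 | 0.864 |

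**Chance of a conflicting result (133 per group, normal approximation).** P = Φ((0.483 − δ)/0.2453) − Φ((0.317 − δ)/0.2453), where δ is the true excess:

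- δ = 0: 0.074
- δ = 0.4: 0.265
- δ = 0.8: 0.074

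**False claims at a true excess of 0.8, if non-significance were taken as non-inferiority.** This reading is an assumption; the protocol does not state it.

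- 133 per group: Φ((0.483 − 0.8)/0.2453) = Φ(−1.29) = 0.098. The CI rule gives 0.025 by construction. A simulation of 400,000 trials gave 0.098 and 0.025.
- 166 per group: Φ((0.432 − 0.8)/0.2195) = Φ(−1.68) = 0.047, against 0.025.
- 133 per group with an assumed larger SD: 0.26 at SD 2.5 and 0.42 at SD 3.0.

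**The opposite conflict.** A result that is significantly worse yet non-inferior needs h < 0.8 − h, that is h < 0.4. With SD 2.0 this is first reached at 194 per group. At 133 per group it needs an SD below 0.4/(1.969 × √(2/133)) = 1.66; at 166 per group, below 0.4/(1.967 × √(2/166)) = 1.85. It cannot arise at the planned size and SD, but at 166 per group a modestly smaller SD would allow it. A significant benefit always meets the criterion, since the upper limit is then below zero.

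**The case against.** The strongest reply is that the protocol, read as a whole, already contains the criterion. Section 2 names the hypothesis, section 3.2 gives the margin, the interval and the rule, and section 3.5 plans both analysis sets. The t-test and the CI use the same estimate and standard error, so the named method is compatible with the rule. Section 3.5 never calls the t-test decisive and never says what a non-significant result would mean. An SAP could spell out the rule, and the 9.8% rests on a reading that no one has stated.

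Much of this is fair. The criterion is missing from section 3.5, not from the protocol. The sample size is sound. The false-claim rate is a conditional illustration, and it falls to 4.7% if nobody drops out. The heading in section 2 and the unstated sign in section 3.2 are minor by themselves.

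The mismatch remains. Section 3.2 explains how the number of elders was reached; section 3.5 says what will be done with the data, and its declared purpose is to detect a difference. Sharing a standard error does not make a test against zero a test against 0.8. This is a method stated for the wrong question, not a detail left for later.

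**Conclusion.** The concern holds. As written, the analysis of the primary outcome does not test the primary hypothesis, and the criterion used for sizing is not carried into the analysis section.

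The conflict between the two rules covers observed excesses of 0.317 to 0.483 surface at 133 per group, or 0.368 to 0.432 at 166, given SD 2.0. At 133 per group the chance of landing there is about 7% if the true excess is 0 or 0.8, and about 26% if it is 0.4. The inflation from 2.5% to 9.8% (4.7% without dropout) applies only if non-significance is taken as non-inferiority. The mismatch itself does not depend on that assumption. Because it concerns the decision rule for the primary outcome, it must be settled before the results by group are known.

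**What to change.** - **Section 3.5:** make the primary analysis the difference in mean number of new root caries surfaces over 24 months, povidone iodine/NaF minus SDF, with a two-sided 95% CI. Conclude non-inferiority if the upper limit is below +0.8 surface. Say which analysis sets decide; requiring the result in both the intention-to-treat and the per-protocol set is the advisable choice, since both are already planned. Keep the t-test against zero only as a superiority test after non-inferiority is shown.
- **Section 3.2:** state the same direction and sign. SDF minus test with the lower limit above -0.8 is equivalent and acceptable if used throughout.
- **Section 2:** state the null as a difference (test minus SDF) of 0.8 or more, and the alternative as a difference below 0.8.

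The cost is wording in three sections. No extra elders, visits or data are needed: 133 evaluable per group already gives 90.1% power for this rule at zero true difference.
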